## **Experimental Group**

The experimental group used exercise intervention BFRT combined with physical release ASTM as the main intervention measure. The training programs applied by BFRT include ankle stability training and ankle joint surrounding muscle group strength training. Ankle stability training mainly uses the tool Bosu ball [37] to intervene in four movements: single leg support training, kick balance training, plank support, and deep squat. Ankle muscle group strength training mainly includes heel lifting training and foot dorsiflexion, eversion, and inversion training with the assistance of elastic band resistance. Due to the fact that most CAI patients have limited dorsiflexion and insufficient valgus force, the focus of the exercise intervention plan is to increase the intensity of dorsiflexion and valgus training.

In this experiment, IASTM used a fascial knife as the treatment tool. There are mainly five types of knives, including C-type scanning knife, B-type bat knife, M-type large M-knife, A-type shark knife, and S-type hook knife. According to the special shape of each knife, their functions and uses are also different. The IASTM intervention was completed before BFRT, with the main purpose of releasing the soft tissues around the calf and ankle joints through physical intervention with a fascial knife, in order to improve ankle pain and restore ankle range of motion

## **Control Group**

The control group of this study consisted of traditional ankle joint stability training and ankle joint peripheral muscle group strength training, with the same specific training plan as the experimental group

#### Research indicators

# Cumberland ankle instability questionnaire

The Cumberland Ankle Instability Tool (CAIT) [42] assessed patients' perception of ankle instability, including the frequency, intensity, and impact of symptoms. CAIT typically includes a specific range of questions, each of which may have different scores. The total score is usually between 0 and 30 points

#### **FAAM Ankle Function Assessment Questionnaire**

Foot and Ankle Ability Measure (FAAM) is a scale used to evaluate ankle joint function, which includes questions about pain, function, and quality of life, and can be used to assess the overall condition of patients with ankle instability. The functional score includes two types of assessments: the functional level of daily life (FAAM-ADL) and the functional level of physical activity (FAAM-SPORT). The score range is usually from 0 to 100, where 100 represents completely normal ankle joint function, and 0 represents extreme restriction or complete inability to use the ankle joint.

## Ankle joint range of motion

This study used a high-precision joint angle measuring ruler to measure the range of motion of different ankle functions in both sitting and supine positions, including measurements of dorsiflexion and plantar flexion of the ankle, as well as measurements of varus and eversion of the foot.

## Ankle joint strength test

The experimental strength data was tested using a handheld digital muscle strength tester (model: FM-204M series muscle strength tester). The measurement unit of this muscle strength tester is N, with a measurement unit range of  $\pm$  50kgf and a measurement accuracy of  $\pm$  0.5% FS (range)  $\pm$  1 digital peak. The measured data includes both peak strength and instantaneous strength values. Therefore, this study used a handheld digital muscle strength tester, where participants sat in a suitable position, fixed the bottom of the instrument on the ground, and then applied force in different directions through their ankles. Measure the maximum force in the dorsiflexion and plantarflexion of the ankle joint, as well as in the abduction and adduction directions of the foot. The strength test for each different exercise segment needs to be completed three times, and the average of the maximum strength values from the three tests is taken.

## Statistical analysis

This study used SPSS 26.0 statistical software for data reading, testing, and statistical analysis.

The general information of the subjects is analyzed using an independent sample t-test. The measurement data conforms to a normal distribution. Because there are three time points (pre intervention, first intervention, and 6-week intervention) in the experimental data for measuring ankle joint function indicators and range of motion indicators, repeated measures analysis of variance is used for data statistics and analysis. Ankle joint strength was only measured at two time points (before intervention and after 6 weeks of intervention), and the data was only analyzed using paired t-tests. P<0.05 is a significant difference with statistical significance.

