## Research process and methods

Method; Select 30-45 subjects with unstable, restricted, or uncomfortable ankle joints as observation subjects, and randomly divide them into ankle joint blood flow restriction training combined with IASTM group (n=10-15), ankle joint blood flow restriction training alone (n=10-15), and traditional ankle strength training (n=10-15). The intervention lasted for 4-6 weeks, once a week. Cumberland ankle instability assessment, FAAM ankle function assessment score, and ankle range of motion measurement were performed at three time points before intervention, after the first intervention, and after 4 weeks/6 weeks of intervention for the three groups. The ankle strength test was only compared and analyzed at two time points before and after intervention.

Process: This study is divided into three stages: pre intervention stage, post initial intervention stage, and post intervention stage. In the pre intervention stage, researchers will conduct preliminary evaluations and data statistics on subjects, including Cumberland ankle instability assessment, FAAM ankle function assessment score, and ankle range of motion measurement. During the intervention phase, participants from each group will undergo a 6-week exercise intervention, with a training frequency of 2 sessions per week and each session lasting 20-30 minutes. During BFRT exercise, a cuff will be wrapped around the proximal one-third of the upper limb of the subject to improve muscle strength and endurance by restricting blood flow. In this state, corresponding ankle training movements (stability training, ankle peripheral muscle group training) will be completed.

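### A two-group t-test is named for the baseline characteristics although three arms are randomised; the effect is confined to the baseline table

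*Combined protocol and SAP*

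**What the plan says.** The Research process and methods section of the combined protocol and SAP sets the sample: "Select 30-45 subjects with unstable, restricted, or uncomfortable ankle joints as observation subjects". It then gives the allocation: "randomly divide them into ankle joint blood flow restriction training combined with IASTM group (n=10-15"), followed by "ankle joint blood flow restriction training alone (n=10-15), and traditional ankle strength training (n=10-15"). The Chinese-language version of that section gives the same three arms and sizes.

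For baseline data, the Statistical analysis section has one sentence: "The general information of the subjects is analyzed using an independent sample t-test". The criterion for all tests is "P<0.05 is a significant difference with statistical significance". The section also asserts normality: "The measurement data conforms to a normal distribution". It names no three-group test for these data, does not say which arms the t-test would compare, and mentions no multiplicity adjustment.

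The Experimental Group section describes blood flow restriction training with IASTM, and the Control Group section describes traditional training. Neither describes the arm that receives blood flow restriction training alone.

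**The concern.** The named test takes two groups and the design has three. An analyst following the plan would have to choose, without guidance, between testing all three pairs, leaving one arm out and merging two arms. These choices give different baseline tables and different error rates.

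At stake is how the baseline table is read. Testing every pair flags chance differences more often than the 5% criterion suggests. Leaving out or merging an arm leaves part of the allocation unexamined. A non-significant result would also be weak evidence of balance at this size: for an assumed true difference of 0.5 SD, a two-sided t-test at 0.05 has power of about 18.5% with 10 per arm and 26% with 15. More basically, if allocation is properly random, any baseline difference arose by chance, so a significance test on it answers no useful question.

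**Working it through.** **Inputs.** Three randomised arms of 10-15 each (Research process and methods). Independent-sample t-test, P<0.05, normal measurements (Statistical analysis).

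**Assumptions.** Two-sided tests (sidedness is not stated), equal arm sizes, continuous normal variables, and general information meaning baseline characteristics.

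**The plan's own figures.** The plan states no error rate for the baseline comparison, so there is none to reproduce. The sample size is consistent: 3 × 10 = 30 and 3 × 15 = 45.

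**Step 1: number of comparisons.** Three arms give 3 × 2 / 2 = 3 pairs. One t-test covers one pair.

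**Step 2: crude bounds if all three pairs are tested at 0.05.** The Bonferroni bound is 3 × 0.05 = 15.0%. Treating the tests as independent gives 1 − 0.95³ = 14.3%. Both overstate the rate, because each arm appears in two pairs.

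**Step 3: allowing for shared arms.** With a common SD σ and n per arm, a pair is significant when |difference in means| / (σ√(2/n)) exceeds the critical value c. At least one pair is significant when the range of the three means, divided by σ/√n, exceeds c√2. This is a studentized-range probability with three groups.

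- Known variance: c = 1.96, threshold 1.96 × √2 = 2.77, probability 12.2%.
- SD pooled over three arms, c = t(0.975, 3n − 3): 11.9% at n = 10, 12.0% at n = 12, 12.0% at n = 15.

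**Step 4: simulation of the pairwise t-test itself.** Each pair uses its own pooled SD, with 400,000 replicates and no true difference (Monte Carlo standard error 0.05 percentage points).

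| n per arm | One pair only | Any of three pairs | One-way ANOVA |
|---|---|---|---|
| 10 | 5.0% | 12.3% | 4.99% |
| 12 | 5.0% | 12.3% | 5.02% |
| 15 | 5.0% | 12.3% | 5.04% |

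The methods agree on about 12% per variable across the planned range of arm sizes, roughly 7 percentage points above a single three-group test.

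**Step 5: does anything depend on the test?** The function and range-of-motion outcomes go to repeated-measures ANOVA, and strength goes to paired t-tests. The Statistical analysis section does not use the baseline result to choose covariates, decide whether an analysis is run, or alter an outcome comparison.

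**The case against.** The strongest reply is that little turns on this. The baseline test feeds no outcome analysis, and if baseline testing is uninformative under randomisation, its exact error rate hardly matters. That stands, and it is why severity is low. It does not remove the mismatch: the sentence cannot be carried out for three arms without an unplanned choice.

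A second reply is that the 12% describes only one way of applying the sentence. This also stands. If a single pair were tested, or two arms merged and compared with the third, there would be one test per variable at 5%. The 12% is therefore not a property of the plan as written.

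A third is that the test suits the two groups described in the Experimental Group and Control Group sections. That may explain where it came from, but the randomisation is stated as three arms in both languages.

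A reader might go further and infer a high chance of a false flag somewhere in the table. At 12% per variable, five independent variables would give 1 − 0.88⁵ = 47%. The documents do not support such a figure. They do not list the variables or suggest that these are independent. The result also moves with the assumed number: about 32% for three variables and 64% for eight. Correct 5% tests would themselves give 14%, 23% and 34% for three, five and eight variables, so much of the total is not due to the choice of the t-test.

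**Conclusion.** The point holds at low severity. The plan names a two-group test for the baseline characteristics of a three-arm randomised trial and does not say how it would be applied. If all three pairs are tested without adjustment, about 12% of continuous variables will show at least one P<0.05 by chance, against 5% for one three-group test. This rests on the assumptions listed with the calculation and on all pairs being tested, which the plan does not state.

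A reader might infer that the outcome results are compromised. The documents do not support that, since no outcome analysis uses the baseline test. The effect is limited to the baseline table and the impression of comparability it gives.

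**What to change.** Replace the t-test sentence with a baseline table showing all three arms (mean and SD, or n and %) without significance tests. If a test is kept, use one three-group test per variable: one-way ANOVA for continuous variables, chi-square for categories. This costs one sentence and needs no new data. The Experimental Group and Control Group sections should be reconciled with the three-arm allocation at the same time.

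Separately, chance imbalance is better handled in the outcome analysis: compare post-intervention outcomes between the three arms with the pre-intervention value as a covariate (ANCOVA). The pre-intervention measurements are already planned, so no extra data are needed, but this is more than a one-sentence edit. A paired t-test takes no covariate, and the repeated-measures ANOVA already includes pre-intervention as a time point, so the outcome analyses would have to be restated. The baseline correction does not depend on this step.

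### At least seven scores in three arms are tested at P<0.05 with no primary outcome, deciding ANOVA effect, arm contrast or multiplicity rule

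*Combined protocol and SAP*

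**What the plan says.** The Statistical analysis section assigns one method to the function and range-of-motion measures because they are taken at "three time points (pre intervention, first intervention, and 6-week intervention": "repeated measures analysis of variance is used for data statistics and analysis". The only criterion for a finding is "P<0.05 is a significant difference with statistical significance".

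The scores covered are defined under Research indicators:
- CAIT, one total score: "The total score is usually between 0 and 30 points".
- FAAM, two scores: "the functional level of daily life (FAAM-ADL) and the functional level of physical activity (FAAM-SPORT".
- Range of motion, four directions: "including measurements of dorsiflexion and plantar flexion of the ankle, as well as measurements of varus and eversion of the foot".

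Research process and methods sets three randomised arms of 10-15 each: BFRT with IASTM, BFRT alone, and traditional strength training. Strength is also measured in four directions, but the Statistical analysis section gives it only paired t-tests.

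On timing, one sentence in Research process and methods puts the last assessment "after 4 weeks/6 weeks of intervention for the three groups", while the next paragraph says "participants from each group will undergo a 6-week exercise intervention". The Statistical analysis section is clear that the last visit is at 6 weeks.

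**The concern.** The rule does not say which result answers the trial's question. Any of seven or more scores can be reported as a success. Within each ANOVA the plan does not say whether group, time or group-by-time decides. A significant time effect alone would satisfy the written rule, although it says nothing about differences between arms. With three arms there are three pairwise contrasts, and none is named.

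The aims do not settle the contrast. Research Objective and Experimental Group centre on BFRT with IASTM, and Control Group describes traditional training. One sentence in Project Summary, however, can be read as comparing conventional training with BFRT alone.

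At stake is the meaning of P<0.05. Under this rule, the chance that a trial with no real arm difference yields something reportable as positive is several times 5%.

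**Working it through.** The documents state no error rate, power, effect size or SD, so there is no figure of the plan's own to reproduce.

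**Count of scores.** CAIT 1 + FAAM 2 + range of motion 4 = 7. This is a minimum: the range-of-motion section mentions sitting and supine positions, and separate values for each would add more. The four strength directions are not counted because they do not enter the ANOVA.

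**Independent tests.** The chance of at least one false positive among k tests at 0.05 is 1 - 0.95^k.
- k = 7 (one effect per score): 1 - 0.95^7 = 0.302.
- k = 14 (group and group-by-time for each score): 1 - 0.95^14 = 0.512.

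**Correlated scores.** Real scores correlate, which lowers these figures. The correlation is not in the documents, so a range was simulated: 7 scores, 3 arms, 3 visits, no arm difference, n = 10 or 15 per arm, 20,000 trials per setting. Visit correlations (assumed) were either 0.9 between the first two visits and 0.5 otherwise, or 0.7 throughout. Group-by-time was tested with the Greenhouse-Geisser correction. The ranges below run over both sample sizes and both visit patterns.

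| Correlation between scores | Any group-by-time P<0.05 | Any group or group-by-time P<0.05 |
|---|---|---|
| 0 | 0.277-0.309 | 0.494-0.510 |
| 0.3 | 0.255-0.279 | 0.461-0.481 |
| 0.5 | 0.222-0.245 | 0.410-0.423 |
| 0.7 | 0.180-0.194 | 0.327-0.347 |

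If the three questionnaire scores correlate at 0.7, the range-of-motion scores at 0.3-0.5 and the two sets at 0.2-0.3, the group-by-time figure is 0.237-0.271. Simulation error is small: at 0.25 the standard error is sqrt(0.25 × 0.75 / 20,000) = 0.003. The group-by-time range of 0.180 to 0.309 is 3.6 to 6.2 times the nominal 0.05.

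**Error after the fix.** One ANCOVA contrast chosen before data are seen has error 0.048-0.053. If the outcome is picked after seeing the data, the same test has error 0.18-0.24 at correlation 0.5-0.7. If the contrast is also picked from two, the error is 0.31-0.39.

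**Power cost of Holm for a non-primary score.** Assumed arm means at 6 weeks are 0, 0.5 and 1.0 SD, with the effect at that visit only, correlation between scores 0.5, and ANCOVA for BFRT with IASTM against traditional training.
- Unadjusted at 0.05: about 69-96%.
- Holm over 7 tests of one contrast: 37-82% if only that score is affected, 46-92% if all are.
- Holm over everything that remains once one score-by-contrast test is primary, 7 × 3 - 1 = 20 tests: about 25-74%, a loss of about 22-45 points.

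**The case against.** The strongest reply is that this is a small exploratory study. Expected results of the study is modest: it hopes to offer ideas and methods. With 10-15 per arm and no explicit claim of confirmed efficacy, formal error control may look out of proportion. The modesty is real, and it is why an exploratory label is the right default for most results. But no section calls the results exploratory, Project Summary looks for empirical support, and the significance rule carries no qualification.

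Three further points stand in part:
- The plan does not literally say that each score is tested separately. That is an inference, though a reasonable one, since no composite or multivariate test is planned.
- Every error rate above depends on assumed correlations and on no arm differing on any score. The direction does not depend on them: within the range examined, no setting comes near 5%.
- The higher figures of 33-51% require a group main effect to count as a finding. The plan neither says that it would nor excludes it, so they are a possibility and not the main estimate.

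**Conclusion.** The gap is real and should be closed before any result is called positive. With n = 10-15 per arm, no true arm difference and correlation between scores of 0 to 0.7, the chance of at least one false-positive group-by-time result is about 18-31%. It is higher if a group main effect may also count.

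A reader might infer more than the documents support:
- *That the error is about 66%, from 7 scores × 3 contrasts = 21 tests (1 - 0.95^21 = 0.659).* The plan specifies no pairwise tests, and that figure also assumes independence.
- *That the analysis visit is undefined.* The Statistical analysis section names 6 weeks; only one phrase in Research process and methods is loose.
- *That repeated-measures ANOVA is invalid here.* It can be valid; what is missing is the effect that decides and the rule across scores.
- *That outcomes were chosen after the data were seen.* Project Deadline gives a trial end date of 30/12/2023, but nothing shows what had been looked at or when.

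**What to change.** Before data are seen:
1. Name one primary outcome (CAIT, for example) at the 6-week visit, and reconcile the 4- or 6-week phrase in Research process and methods.
2. Reconcile the aims in Project Summary, Research Objective, Experimental Group and Control Group, and name one primary arm contrast consistent with them. BFRT with IASTM against traditional training would match the experimental and control labels.
3. Test that contrast at 0.05, preferably by ANCOVA on the 6-week score with the baseline score as covariate. This is an efficiency gain, not a validity correction. If repeated-measures ANOVA is kept, name group-by-time as the deciding effect and apply the Greenhouse-Geisser correction.
4. By default, label all other outcomes and contrasts exploratory. This includes the four strength directions, whose paired t-tests contain no arm contrast. If Holm is used instead, define the family and state its power cost as set out above.

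Cost: wording only, with no new data. ANCOVA at 6 weeks can lose some power relative to group-by-time if the full effect is already present after the first session. The loss was about 8 points in one simulated pattern (0.739 against 0.815) and about 11 in another (0.782 against 0.891), so neither figure is an upper bound.

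If data are already collected, date the change, label it post hoc and present all results as exploratory. Naming a primary outcome at that stage does not restore the 5% error rate, so the cost is the confirmatory claim itself.

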**Table 1 Inclusion and Exclusion Criteria** 

Standard	Inclusion Criteria	Exclusion Criteria	
Age	118-35 years old	under 18 years old or above 35 years o	
Course Of	Suffering from chronic ankle instability	Acute ankle injury or no joint injury	
Disease	symptoms that last for at least 3 months		
CAIT score	The CAIT score is 24 points or less.	CAIT score above 24 points	
Functional	Two or more tests tested positive for ankle	Failed ankle function screening	
screening	joint function screening before the		
	experiment		
Structural	No structural joint lesions or congenital	Structural lesions or congenital ankle	
inspection	ankle deformities,	deformities present in the ankle joint	
Medical	Have not undergone ankle surgery or have	Have undergone ankle surgery or have obvious	
History	external injuries	injuries or wounds	
Health	No serious heart, lung, nervous system or	Serious heart, lung, nervous system or other	
Condition	other systemic diseases	systemic diseases	
Agree to	Limited athletic ability, unable to complete	Disagree to participate in the study, or inability	
participate in	research tasks	to understand and comply with the research	
research		protocol	

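### The pre-treatment CAIT, FAAM and range-of-motion values enter the repeated-measures ANOVA as an outcome rather than a covariate, which costs the arm comparisons some precision

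*Combined protocol and SAP*

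**What the plan says.** Under Research process and methods, three randomised arms of 10 to 15 have CAIT, FAAM and range of motion assessed "before intervention, after the first intervention, and after 4 weeks/6 weeks of intervention". The Statistical analysis section gives one analysis for these outcomes: "repeated measures analysis of variance is used for data statistics and analysis". Its reason is the number of visits: "Because there are three time points (pre intervention, first intervention, and 6-week intervention) in the experimental data". The pre-treatment reading is therefore a level of the response.

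The section does not mention a baseline covariate, analysis of covariance or a mixed model. It does not say whether the group effect, the group-by-time effect or some contrast answers the treatment question, and it asks for no estimate or interval. It also asserts: "The measurement data conforms to a normal distribution". Table 1 restricts entry by CAIT: "The CAIT score is 24 points or less". FAAM and range of motion have no such cut.

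Strength is analysed separately, by paired t-tests, and lies outside this point.

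**The concern.** Randomised arms can differ before treatment only by chance, so the pre-treatment reading says nothing about the treatment effect. Its use is to explain variation in the later readings. Entered as a response, it does not do that job well. The group effect averages in a visit at which no effect is possible. The baseline-to-final part of the group-by-time effect compares unadjusted changes, which carry the full noise of the baseline reading. Group-by-time also combines the reading after the first session with the final one, so it does not isolate the end-of-programme difference.

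At stake is the precision of the arm comparisons for function and range of motion, two of the three outcome areas in the Research Objective. The arms are small and the documents give no sample-size justification.

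**Working it through.** The plan states no power, effect size, SD or correlation, so there is no figure of its own to reproduce.

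**Inputs from the documents.** Three arms; n = 10 to 15 per arm, so N = 30 to 45; significance at 0.05 (two-sided assumed).

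**Assumptions.** Baseline-to-final correlation r from 0.4 to 0.7, with 0.9 and 0.95 as extremes; equal SDs at baseline and final visit, except where stated; effects in SD units.

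**Precision of one pairwise arm difference at the final visit, in SD² units.**
- Unadjusted change: 2(1−r) × 2/n.
- Baseline-adjusted: (1−r²) × 2/n.
- Ratio: (1−r²) / [2(1−r)] = (1+r)/2.
- Cost of estimating the baseline slope, pooled over three arms: a variance factor of 1 + 1/(N−5), which is 1 + 1/25 = 1.04 at N = 30 and 1 + 1/40 = 1.025 at N = 45.

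Interval narrowing is 1 minus the square root of the variance ratio:

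| r | (1+r)/2 | × 1.04 | narrower, 10 per arm | × 1.025 | narrower, 15 per arm |
|---|---|---|---|---|---|
| 0.4 | 0.70 | 0.728 | 15% | 0.718 | 15% |
| 0.5 | 0.75 | 0.780 | 12% | 0.769 | 12% |
| 0.7 | 0.85 | 0.884 | 6% | 0.871 | 7% |
| 0.9 | 0.95 | 0.988 | 1% | 0.974 | 1% |
| 0.95 | 0.975 | 1.014 | none | 0.999 | none |

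**Power for a 1.0 SD pair at r = 0.5 (simulation, error pooled over three arms).** Change against adjusted: about 58% against 69% at 10 per arm, and about 77% against 87% at 15. Repeat runs agree within about two percentage points.

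**Omnibus tests.** Final-visit arm means were 0, 0.5 and 1.0 SD, with no effect at the second visit and all correlations 0.5. Group-by-time against adjusted final visit gave 48% against 56% at 10 per arm, and 69% against 78% at 15. If the first two visits correlate 0.85, the two tests nearly tie at 10 per arm (56% and 57%), but the pairwise gain remains (59% to 69%). Type I error was 4.7% to 5.3% for every method.

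**CAIT.** The entry cap shrinks the baseline SD. Take a normal baseline with SD 1 before the cut, cut at its 80th percentile or its median (both assumed). Its variance after the cut is k² = 1 − cλ − λ², where c is the cut point and λ the normal density at c divided by the retained fraction.
- 80th percentile: c = 0.842, λ = 0.350, k² = 0.583.
- Median: c = 0, λ = 0.798, k² = 0.363.

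With uncut r = 0.5, the change variance is (1−r)²k² + (1−r²), and the adjusted variance at N = 30 is 0.75 × 1.04 = 0.780.
- 80th percentile: 0.25 × 0.583 + 0.75 = 0.896; 0.780/0.896 = 0.871; about 7% narrower.
- Median: 0.25 × 0.363 + 0.75 = 0.841; 0.780/0.841 = 0.928; about 4% narrower.

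Power for a 1.0 SD pair at 10 per arm then goes from about 62% to 68%, or from 65% to 67%. At uncut r = 0.7 the narrowing is about 3% or 1%.

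**The case against.** The strongest reply is that the planned test is valid and the gain is of unknown size. That stands in part. The documents give no r, the gain is negligible at 0.9 and absent near 0.95 with 10 per arm, and adjustment is not literally free. The equal-SD assumption also matters. If the baseline SD is 0.7 of the final SD and r = 0.5 in the trial sample, the change variance is 0.49 + 1 − 0.70 = 0.79 against 0.780 adjusted at N = 30, almost no gain.

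A second reply is that group-by-time is the natural test in a pre/post design and suffers least. That also stands: its disadvantage shrinks to almost nothing when the first two visits are highly correlated, which is plausible when only one session lies between them. What remains is the loss in the pairwise comparisons.

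Stronger readings are tempting, but the documents do not support them.
- A reader might infer that the trial has only 11% to 15% power, since the group effect reaches no more when r = 0.5 and the effect appears only at the final visit. The plan does not name that term as the test. With effects at both post-treatment visits its power is 32% at 10 per arm and 47% at 15.
- A reader might infer that the cap at 24 invalidates the ANOVA because baseline CAIT cannot be normal. No bounded score is exactly normal, no effect on error rates has been shown, and the adjusted model also needs well-behaved residuals.
- A reader might conclude that the three-visit analysis should become purely descriptive. That would leave the planned assessment after the first session without an arm comparison.

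**Conclusion.** The point holds as a modest, worthwhile efficiency improvement. The direction is secure in the usual range of correlations: using the baseline as a response gives less precise pairwise arm comparisons than using it as a covariate. It causes neither bias nor inflated type I error.

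The size rests on assumptions. With equal SDs and r between 0.4 and 0.7, intervals narrow by about 15% down to 6%. The estimate suits FAAM and range of motion best, as they have no entry cut. For CAIT, about 4% to 7% is more realistic at r = 0.5, depending on where the cap falls in the distribution of baseline scores. No single figure should be quoted for all outcomes.

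**What to change.** In the Statistical analysis section, take the arm comparisons for CAIT, FAAM-ADL, FAAM-SPORT and each range-of-motion direction from a model with that outcome's own pre-treatment value as covariate. Either form serves:
- the final-visit value on arm and baseline; or
- both post-treatment visits on arm, visit, arm-by-visit and baseline, allowing for correlation within participant.

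The second form keeps an arm comparison at the visit after the first session. Report each pairwise arm difference with its 95% CI. Replace the statement that the data are normal with a check of the model residuals.

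The cost is one error degree of freedom, a variance factor of about 1.03 to 1.04, and an assumed straight-line relation with baseline. No further participants, visits or measurements are needed. If the data have already been analysed, the adjusted model can be run on them and reported as a departure from the plan.
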